This study is an open-label, randomized controlled trial. Patients will be randomized into two groups of 15, "Routine Care" group, which will serve as the control group, and "Octreotide" group. The amount of bronchial secretions is routinely measured in all mechanically ventilated patients. Once the Primary Team identifies a patient as a candidate for the study, the study team will review their medical records and assess the patient based on the inclusion and exclusion criteria to determine if they are qualified to participate in the study (screening). If the patient is qualified, one of the study members will explain the research project to the patient or his/her authorized representative and also explain the informed consent process. This study does not compensate patients for participating in the study or for any potential injuries/illness arising out of their participation in this study. This aspect will be made clear to the patients (or their authorized representative) in addition to other risks and benefits of participation in this study. If the patient or his/her authorized representative agrees to participate in the study informed consent will be obtained. After informed consent, the patient will be administered

standard of care medications for the first 24 hours after the screening and a baseline volume of bronchial secretions during this 24 hour period will be recorded. Additionally, medications administered and procedures performed during this 24 hour period would also be recorded. Then, a security envelope containing group assignment will be opened by the ICU attending physician. Both groups will continue to receive treatments that have already been initiated to manage bronchial secretions. In addition, "Octreotide" group will receive parenteral octreotide, while "Routine Care" group will not receive any additional treatment for the study. All patients will continue to receive the care deemed necessary by the ICU attending physician and his/her team. These interventions will be continued for 72 hours or until extubation or withdrawal from the study, whichever occurs earlier. Subsequently, the standard of care management, as determined by the Primary Team, will be continued.

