Medications and procedures performed as part of the standard of care while the patient is on octreotide (for the "Octreotide" group) and 24 hours after admission (for the "Routine Care" group) will be recorded for the next 72 hours or until extubation or withdrawal from the study, whichever occurs earlier. Additionally, for patients in the "Octreotide" group, the rate, dose and mode of octreotide administration will be recorded on an octreotide administration log. The rate of bronchial secretions will be measured and recorded twice daily; the changes, relative to the baseline measurements, will be compared between the groups.

[figure not shown]

Figure 1. Trial design.

Electronic medical records of the subjects will be retrospectively reviewed to collect the following data recorded by the Primary Team during the ICU stay: demographic information, past medical history, smoking history, diagnoses and problem list, vital signs, diagnostic test data, medications, and procedures performed during the entire length of stay during which the subjects participated in the study.

If a patient has decision-making capacity, an informed consent will be obtained from the patient. Otherwise, an informed consent will be obtained from the person who has a legal authority to make healthcare decisions for the patient.

To minimize bias, patients will be randomized into the two groups of 15 using a random list generator (<http://www.random.org/lists/>). The research coordinator will be responsible for maintaining randomization and will place treatment assignments into security envelopes, which will be stored in the ICU intensivist workroom with code-protected entrance.

Each participant's involvement in the study is expected to last approximately 72 hours, plus the time that is necessary to ensure accurate measurement of baseline secretions rate (for up to 24 hours).

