Also, subjects in both groups will be at risk that their bronchial secretions are not well controlled. However, it is expected that at the time of enrollment, the subjects will already be receiving nebulizer treatments, which is the standard of care for management of mechanically ventilated patients; the study will compare additional interventions for which no quality evidence-based data exists so far.

Subjects may benefit from this study by experiencing better control of their bronchial secretions, which may shorten duration of mechanical ventilation and decrease risk for related complications. The information learned from this study may help other patients requiring mechanical ventilation.

Selection and Withdrawal of Subjects:

Inclusion criteria:

- Patients are being weaned from mechanical ventilation
- Excessive bronchial secretions (over 200 ml/24 hours) is deemed by the Primary Team to be a major barrier to extubation

Exclusion criteria:

- Known hypersensitivity to octreotide
- Persistent bradycardia (HR < 60)
- Mobitz type II or 3rd degree heart block in patients without a pacemaker
- Active septic shock
- Patients being treated with intravenous agents for hypertensive urgency or emergency
- Cardiac surgery patients
- Initiation of therapy with systemic or inhaled steroids within 72 hours prior to screening*
- Initiation of therapy with systemic or inhaled anticholinergics within 48 hours prior to screening*
- Patients receiving cyclosporine, bromocriptine, or drugs with low therapeutic index that are mainly metabolized by CYP3A4

*Initiation of aerosolized (inhaled) anticholinergics or steroids will not be withheld to qualify a subject for the study. Once a mechanically ventilated patient has been on an anticholinergic for more than 48 hours or a steroid for more than 72 hours, he or she will no longer meet that exclusion criteria and may be included in this study with appropriate debriefing about the study by the study team to the patient or their authorized representing and obtaining informed consent.

Withdrawal of subjects:

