If a patient develops bradycardia (HR < 60 bpm), octreotide administration will be stopped and the patient will be withdrawn from the study. Furthermore, if a subject experiences increase in systolic BP to 180 mmHg or above, octreotide administration will be stopped and the patient will be withdrawn from the study. However, if a subject experiences increase in systolic BP by at least 40mmHg over 2 hours, the infusion rate will be decreased to 12 mcg/hr; the BP will be reassessed every hour, and the infusion rate will be titrated up as tolerated to a maximum of 25mcg. Given octreotide's effect on serum glucose level, all subject's capillary blood glucose (CBG) will be monitored every 4 hours to monitor for hyperglycemia and hypoglycemia. The glucose levels every 4 hours will be recorded in the data collection form. Subjects who are hyperglycemic and require more than 20 units of intravenous insulin per hour will be withdrawn from the study, as will subjects who experience hypoglycemia (CBG < 60 mg/dL) despite being on 5% dextrose drip.

Statistical analysis:

Data will be analyzed with the assistance of a statistician at Danbury Hospital's Department of Research and Innovation. The differences between the two groups (Routine Care vs. Octreotide) in the percentage change of rate of secretion (defined as milliliters per 24 hours) for each of the 24-hour periods as compared to the baseline 24-hour period and proportion of patients extubated within 72 hours (defined as both time to extubation AND yes/no extubated within 72 hours) will be compared. The Fisher's exact test will be used to assess statistical significance (alpha set at $p < 0.05$). If the sample size allows and there are adequate cell frequencies, regression analyses will be used to assess the association between the use of Octreotide and the primary outcome variables.

Given that no previous research has been conducted to examine management of bronchorrhoea resistant to conventional interventions in mechanically ventilated patients, a power calculation to estimate the sample size cannot be performed reliably. We do recognize the small sample size to be included in our study and intend for this project to serve as a pilot study that would provide some evidence-based information to guide clinicians at our institution in such situations and provide background information for further studies on a much larger scale.

References:

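### No heart-rate or systolic-pressure condition is attached to opening the envelope, so octreotide can be started at values the plan later uses to stop it

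*Combined protocol and SAP*

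**What the plan says.** **Entry (Selection and Withdrawal of Subjects, exclusion criteria).** The heart-rate criterion is "Persistent bradycardia (HR < 60" bpm, with no duration or number of readings to define 'persistent'. The only blood-pressure criterion is defined by treatment: "Patients being treated with intravenous agents for hypertensive urgency or emergency". No value in mmHg is given.

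**Screening and monitoring (Trial Design; Assessment of Safety).** Before consent the study team reviews the record and assesses the patient against the criteria. An ECG is reviewed for each subject. Patients with bradycardia or significant conduction defects are said to be excluded, with a reference back to the exclusion list. Heart rate is monitored continuously and other vital signs hourly.

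**Allocation (Trial Design).** After consent the patient receives "standard of care medications for the first 24 hours after the screening" while baseline secretions are measured. "Then, a security envelope containing group assignment will be opened by the ICU attending physician". No vital-sign condition or eligibility recheck is stated here, or in Treatment of Subjects before the 12 mcg/hr start.

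**Stopping (Assessment of Safety).** For heart rate: "If a patient develops bradycardia (HR < 60 bpm), octreotide administration will be stopped and the patient will be withdrawn from the study". For pressure: "if a subject experiences increase in systolic BP to 180 mmHg or above, octreotide administration will be stopped", again with withdrawal. A third rule lowers the infusion rate "if a subject experiences increase in systolic BP by at least 40mmHg over 2 hours".

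**The concern.** The sponsor chose a heart rate of 60 and a systolic pressure of 180 mmHg as the points at which octreotide should not continue. Nothing in the entry or allocation steps prevents the drug from being started beyond those points, and about 24 hours pass between screening and allocation.

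Two things are at stake. The first is safety at the first dose. For a patient already at or above 180 mmHg the team has no clear instruction. The matter is sharper for the subcutaneous route, because an injected dose cannot be taken back.

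The second is where the loss falls. The stops are written around stopping octreotide, so a withdrawal prompted by a value present before treatment would fall on the octreotide arm, after allocation is known, in an open-label trial. The same patient held back before the envelope is opened causes no imbalance between arms.

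**Working it through.** The plan gives no figure to reproduce, so the check sets entry, start and stop conditions side by side.

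| | Exclusion at entry | Condition at envelope or first dose | Stop and withdraw |
|---|---|---|---|
| Heart rate | < 60, only if persistent | none stated | develops < 60 |
| Systolic pressure | no value; intravenous treatment for urgency or emergency only | none stated | increases to >= 180 mmHg |

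**Heart rate.** A non-persistent value below 60 passes entry, and nothing is asked at the envelope. The ECG statement in Assessment of Safety omits 'persistent', but it defers to the exclusion list and gives no time for the review.

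**Systolic pressure.** A patient at, say, 185 mmHg on oral drugs or none passes entry. Both pressure rules are worded as rises, so a high value that is already present and stays level is not clearly covered by either. The 40 mmHg rule reduces the infusion only to 12 mcg/hr, which is already the starting rate.

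**Subcutaneous dose.** Treatment of Subjects splits the daily dose into two 12-hourly injections. At the BMI-based target rates of 18 to 24 mcg/hr, each injection is 18 × 12 = 216 mcg to 24 × 12 = 288 mcg. Stopping prevents the next injection only.

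**Size, with 15 per group (Trial Design).**
- One withdrawal: 1/15 = 6.7% of the octreotide arm. Two: 2/15 = 13.3%. These are sizes per patient, not estimates of frequency.
- Precision, assuming equal SDs and that withdrawn patients are left out of the analysis: the ratio of the standard error of a difference in means to its 15 v 15 value is sqrt((1/n + 1/15)/(2/15)).
  - n = 14: sqrt((1/14 + 1/15)/(2/15)) = 1.018, a rise of 1.8%.
  - n = 13: sqrt((1/13 + 1/15)/(2/15)) = 1.038, a rise of 3.8%.

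**Data available for a check.** Trial Design counts the baseline as part of participation: about 72 hours "plus the time that is necessary to ensure accurate measurement of baseline secretions rate (for up to 24 hours". If hourly monitoring applies from then, up to 24/1 = 24 readings exist before the envelope is opened, or 24/4 = 6 at the four-hourly recording interval.

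**The case against.** The strongest case on the other side is that entry and stopping rules do different jobs. Entry screens out a standing condition; stopping reacts to a new change on the drug. A stricter rule on treatment is a legitimate choice. Patients are assessed as well as chart-reviewed, an ECG is read, and monitoring is continuous or hourly. The study team may take remedial measures, and the ICU attending physician opens the envelope. On this view surveillance is complete and only a written trigger is missing. The number affected may be zero, and one-sided withdrawals on treatment would continue in any case.

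Most of this stands. The difference in wording between entry and stopping is not an error in itself, and there is good reason to keep 'persistent' so that one transient dip does not exclude a patient. Detection is likely.

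What the objection does not supply is an instruction. Monitoring shows the value; the protocol does not say what to do with it before allocation. Without a rule, the decision to withhold or give the first dose would be made after the assignment is seen, possibly by an attending physician who is also an investigator, an overlap that Trial Design allows.

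A reader might infer that the plan contradicts itself by starting the drug at a value where it orders a stop. The text does not support that. The stops are worded as a patient developing bradycardia or having an increase to 180 mmHg, so for a value present at the start the plan is unclear rather than contradictory. A reader might also infer a material loss of power or a demonstrated bias. Nothing in the documents gives a frequency from which to argue either.

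**Conclusion.** The gap is real and limited. As written, the plan allows a patient to be randomised and started on octreotide with a heart rate below 60 that is not persistent, or with a systolic pressure of 180 mmHg or more and no intravenous agent. It does not clearly say what follows.

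The conclusion rests on reading the exclusion list literally and on the absence of any recheck in Trial Design or Treatment of Subjects. It does not assume that such patients will occur. The precision cost is minor and would apply only if withdrawn patients were left out of the analysis, which the protocol does not settle for these withdrawals. The case for change is a safe first dose and a decision taken before allocation is known. It is a cheap improvement that should be made, not a flaw that undermines the trial.

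**What to change.** In Trial Design, at the step where the envelope is opened, add:

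*Immediately before the envelope is opened, the latest charted values must be HR >= 60 and systolic pressure < 180 mmHg. If not, opening is deferred; if the values have not resolved within a stated limit (for example 24 h), the patient is not randomised. If opening is deferred, the most recent 24 h secretion volume before opening is used as the baseline.*

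The last sentence is needed because the primary outcome is percent change from baseline, and a deferral would otherwise separate the baseline from the start of treatment. Keep 'persistent' in the exclusion list as the screening criterion, and leave the stopping rules in Assessment of Safety unchanged.

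The cost is a short insertion, a look at values already charted, and secretion measurement continued through any deferral; Trial Design says secretions are measured routinely in ventilated patients. A few patients will be delayed or not enrolled. Because allocation is still unknown, the rule applies equally to both arms. It prevents starts at a stopping value. It does not prevent later dips or drug-induced withdrawals on treatment.

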While enrolled in the study, management of medical problems other than increased bronchial secretions will not be affected by participation in the trial, and the subjects will receive all the interventions that are recommended by the Primary Team. Management of bronchial secretions, using non-pharmacologic and pharmacologic interventions, is an essential element of care for all mechanically-ventilated patients. This includes anticholinergics, glucocorticoids, and β_2 -adrenergic agonists that can be used, if indicated, to regulate mucus production; they are usually administered in aerosolized form according to a respiratory-therapy driven protocol. However, some patients experience excessive bronchial secretions (bronchorrhea) despite these interventions. Currently, there are no evidence-based guidelines and no institutional protocol to guide clinicians in such situations. The standard of care to manage excessive bronchial secretions may vary among patients. For "Routine care", some physicians may continue previously started interventions such as inhaled medications (beta-agonists, anticholinergics, and corticosteroids), while others may also use systemic steroids, systemic anticholinergics, or macrolide antibiotics. It has to be noted that some of these standard of care treatment options may also not have a strong research validation to support their use¹⁵.

It is possible that the members of the primary team and the study team overlap, meaning that the ICU attending physician and residents who are part of the primary team for a given study subject may as well be the PI or the co-investigators in this study. The following are the study related responsibilities of the study team staff, irrespective of whether they are part of the primary team or not.

1. After initial alert from the Primary team, review patient medical record for exclusion/inclusion criteria, discuss the study including the fact there is no compensation for illness/injury related to the study to the patient or authorized representative and if the patient (or representative) agrees to participate, obtain informed consent and enroll the in the study.
2. Assign and monitor randomization

3. Obtain baseline sputum collection.
4. Assess the dosage of octeroide infusion within the range prescribed in this study, document and monitor the administration.

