If, for any reason, a subject or his/her legal representative chooses to discontinue involvement in the study at any time, they may do so by informing the study doctor (PI [name]) his or her wishes. In this case, all the interventions related to the study and prospective collection of study-related data will be stopped, and the standard of care management, as determined by the Primary Team, will be resumed. Only the data that has already been prospectively collected, along with the data obtained from retrospective chart review, will be used.

If, during the trial, starting treatment with a medication that can affect bronchial secretions is indicated for a medical condition other than increased bronchial secretions, the subject will be withdrawn from the trial. These medications are as follows: inhaled bronchodilators, inhaled or systemic anticholinergics, inhaled or systemic steroids, and octreotide.

Treatment of Subjects:

Subjects in the "Routine Care" group will receive interventions as deemed necessary by the Primary Team, which should be no different from patients not participating in this study. No evidence-based guidelines have been established for management of excessive bronchial

secretions that have not responded to standard interventions, such as nebulizer treatments. Use of systemic anticholinergics (scopolamine and glycopyrrolate) and systemic steroids have been described in case reports.

Subjects in the “Octreotide” group will receive parenteral octreotide, either as intravenous infusion (preferred option) or subcutaneously (if the previous option is not feasible). The therapeutic rate of intravenous infusion is 12-25 mcg/hour. The initial rate will be 12 mcg/hr, which will be titrated up every 3 hours by 4 mcg/hr to reach the target rate of 18 mcg/hr for patient with BMI < 26, 20 mcg/hr for patients with BMI of 26-30, or 24 mcg/hr for patients with BMI > 30. The team will adjust the infusion rate based on renal/hepatic function (per recommendations of a pharmacist) and in response to side effects but will not exceed 25mcg/hr for any subject. If intravenous infusion is not feasible, octreotide will be administered subcutaneously, with daily dose (as determined above for the intravenous infusion) divided into 2 doses given every 12 hours.

Octreotide administration will be completely stopped, if a subject develops a clinically significant adverse reaction that has not responded to decreasing the infusion rate.

Assessment of Efficacy:

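### Does a fixed 4 mcg/hr titration step put the 18 mcg/hr target for BMI < 26 out of reach?

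*Combined protocol and SAP*

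**What the plan says.** The dosing rule is in Treatment of Subjects. For the intravenous route, "The initial rate will be 12 mcg/hr", and it is then "titrated up every 3 hours by 4 mcg/hr to reach the target rate of 18 mcg/hr for patient with BMI < 26". The other two targets follow in the same sentence: "20 mcg/hr for patients with BMI of 26-30, or 24 mcg/hr for patients with BMI > 30". One step size and one interval serve all three groups.

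The next sentence allows individual departures: "The team will adjust the infusion rate based on renal/hepatic function", on a pharmacist's advice, and also in response to side effects, "but will not exceed 25mcg/hr for any subject".

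Three other places bear on the point:

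- Trial Design, in the list of study-team duties (item 4), has the team "Assess the dosage of octeroide infusion within the range prescribed in this study, document and monitor the administration". It gives no step size.
- Trial Design also says that, for the octreotide group, "the rate, dose and mode of octreotide administration will be recorded on an octreotide administration log".
- Assessment of Safety covers a rise in systolic pressure of at least 40 mmHg over 2 hours. The rate is cut to 12 mcg/hr, pressure is rechecked hourly, and "the infusion rate will be titrated up as tolerated to a maximum of 25mcg".

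**The concern.** A schedule that fixes a start, a step and an end point should have an end point that the step can reach. Two of the three targets pass that test and the third does not. Taken literally, a patient with BMI < 26 cannot both move in 4 mcg/hr increments and arrive at 18 mcg/hr. Someone who held to the step would stop short at 16 or go on to 20, and 20 is the rate assigned to the next BMI group. The stated reasons for adjusting the rate (renal or hepatic function, side effects) do not cover a patient who is simply following the schedule.

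A second question sits beside it. The re-titration text in Assessment of Safety names only the 25 mcg/hr ceiling and does not say whether the BMI target still applies.

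At stake would be uniform delivery of the only experimental treatment, in an arm of 15 patients. If dose entered the analysis, its interpretation would be at stake too.

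**Working it through.** **Inputs** (all from Treatment of Subjects): start 12 mcg/hr; step 4 mcg/hr every 3 hours; targets 18, 20 and 24 mcg/hr; ceiling 25 mcg/hr.

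**Rates reachable in whole steps:** 12 + 4k, up to the ceiling, gives 12, 16, 20, 24.

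**Steps needed:** (target − 12) / 4.

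| BMI group | Target (mcg/hr) | Steps | Reached in whole steps? |
|---|---|---|---|
| < 26 | 18 | (18 − 12)/4 = 1.5 | No |
| 26-30 | 20 | (20 − 12)/4 = 2 | Yes, at hour 6 |
| > 30 | 24 | (24 − 12)/4 = 3 | Yes, at hour 9 |

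The observation is therefore correct: 20 and 24 reproduce and 18 does not. After one whole step the rate is 16, and 18 − 16 = 2 mcg/hr remains.

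**Three ways to read the sentence for BMI < 26:**

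1. Titration ends at the target. The increment due at hour 6 is 2 instead of 4 mcg/hr, and the difference from 18 is zero.
2. Whole steps, not passing the target: the rate stays at 16, and 16/18 = 0.89.
3. Whole steps until the target is met or passed: the rate becomes 20, and 20/18 = 1.11.

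**Outer bound on cumulative dose**, assuming a full 72-hour infusion with no other rate change:

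- Reading 1: 12×3 + 16×3 + 18×66 = 1,272 mcg
- Reading 2: 12×3 + 16×69 = 1,140 mcg
- Reading 3: 12×3 + 16×3 + 20×66 = 1,404 mcg

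Readings 2 and 3 each differ from reading 1 by 132 mcg, and 132/1,272 = 10.4%. An infusion that ends earlier gives a smaller percentage, because the readings part only at hour 6.

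**Does any of this reach the analysis?** Assessment of Efficacy defines the primary outcome as percent change in secretion rate from baseline, octreotide against routine care. The secondary outcome is the proportion extubated within 72 hours. Statistical analysis plans Fisher's exact test and, if numbers allow, regression on use of octreotide. None of these takes infusion rate, cumulative dose or BMI as an input. The same section says that no reliable power calculation could be made, so there is no assumed dose effect to disturb.

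**Re-titration after a pressure rise.** Treatment of Subjects caps every subject at 25 mcg/hr, and Assessment of Safety gives the same 25 as the maximum. The two agree. A ceiling says how far the rate may go and does not cancel a target set elsewhere.

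**The case for a change.** The best case for a change is that an infusion schedule should be executable as written for every patient, and that here the last increment for one BMI group is implied and not stated. Readings 2 and 3 both fall inside 12-25 mcg/hr, so the range limit would not flag either. The administration log would show which rate was given, but the protocol would not settle whether 16 or 20 counted as a deviation. The trial is offered as a pilot for larger studies, so the sentence may be reused. After a pressure-triggered cut, silence about the BMI target leaves 25 against 18 mcg/hr (25/18 = 1.39) open to argument. A correction would cost only wording.

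Part of this stands. The shorter increment is nowhere written, and the re-titration text does not mention the BMI targets. But readings 2 and 3 need staff to stop short of, or run past, a rate the protocol names, and nothing in the documents suggests that they would. The figures 12, 4, 18, 20 and 24 are specifications and not results of a calculation, so no sum has been done wrongly. On re-titration, the two sections state the same ceiling, so no contradiction is shown. A low cost of editing does not by itself make a reason to change the plan when no result would differ.

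**Conclusion.** The mismatch is real as arithmetic and harmless as a plan. The sentence gives the step as the means and the target as the end, and a reader who ends titration at the target has a workable schedule for all three BMI groups. This is a detail that staff fill sensibly.

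Even on the strained readings, the difference is 2 mcg/hr (11% of 18), or at most 10.4% of the 72-hour total. It is confined to octreotide-arm patients with BMI < 26 treated intravenously. Their number cannot be derived, because the protocol gives no BMI distribution. Every candidate rate lies within the stated range and would be recorded.

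The estimate, the tests and the conclusions would be the same whichever way the sentence were worded. That rests on the analyses staying as described, with no dose-response or BMI-specific comparison. It implies no opinion on which step, target or re-titration limit is clinically right.
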